3.2 Determination of Sample Size

Approximately 210 patients may be enrolled in a 1:1 ratio to LY3127804 or placebo (105 per treatment group) in order that 200 patients complete the study. A sample size of 100 in each group will have 81% power to detect a difference between the placebo group and the LY3127804 group using a Wilcoxon rank-sum test with a 0.05 one-sided significance level. This powering is based on the following assumptions: intermittent mandatory ventilation (IMV) rate of 25% and mortality rate of 12.5% in the placebo group, 50% improvement in IMV rate and mortality rate for the LY3127804 group relative to placebo, and a mean difference (LY3127804 minus placebo) of 3.0 ventilator-free days where patients who die are assigned a value of -1.

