3.3 Method of Assignment to Treatment

Patients who meet all criteria for enrollment will be stratified by age group (<65 years and ≥ 65 years), sex, and site, and then, on Day 1, randomly assigned in a 1:1 ratio within each stratum to receive either LY3127804 or placebo. Treatment assignment will be determined by a computer generated randomization sequence using an interactive web response system (IWRS).

4. A Priori Statistical Methods

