Unless otherwise noted, treatment comparisons of quantitative variables will be made using a restricted maximum likelihood-based mixed-effects model of repeated measures (MMRM). The model will include treatment, age group, sex, and site as fixed categorical effects, and, if applicable, study day as a continuous effect and treatment-by-study day interaction. The covariance structure to model the within-patient errors will be unstructured. If the available data cannot support the covariance structure (e.g., due to missing values), other structures will be attempted. If the unstructured covariance matrix results in a lack of convergence, the heterogeneous Toeplitz (TOEPH) covariance structure, followed by the heterogeneous autoregressive [ARH(1)] covariance structure, followed by the compound symmetry structure will be used. The first structure to yield convergence will be used for inference. The NewtonRaphson with ridging optimization technique will be used to aid with convergence. The Kenward-Roger approximation (KR2) will be used to estimate the denominator degrees of freedom and adjust standard errors. Type III tests based on the LS means will be used for the statistical comparison; the 90% CI will also be reported.

All tests of treatment effects will be conducted at a 1-sided alpha level of 0.05, unless otherwise stated. No adjustments for multiple comparisons will be made.

All computations for statistical analyses will be performed using SAS® software, Version 9.4 or later. All SAS programs used in the production of statistical summary outputs will be validated with independent programming prior to finalization. In addition, all program outputs will be independently reviewed. The validation process will be used to confirm that all data manipulations and calculations were accurately done. Upon completion of validation and quality review procedures, all documentation will be collected and filed by the project statisticians.

When implementing parametric methods of analysis, the distribution of analysis variables will be examined to determine if model assumptions are satisfied. Transformations or nonparametric methods of analysis may be added as sensitivity analyses if warranted. Whenever alternative methods of analysis are required, the description of the new method along with the rationale for its use will be documented in the Clinical Study Report (CSR).

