4.12.3.2 NIAID Ordinal Assessment

The NIAID will be assessed daily and defined as the lowest score achieved for that day.

The scoring is based on the clinical status of the patient as described below.

NIAID Score	Description
1	Death

2	Hospitalized, on invasive mechanical ventilation or extracorporeal membrane oxygenation (ECMO)
3	Hospitalized, on non-invasive ventilation or high flow oxygen devices
4	Hospitalized, requiring supplemental oxygen
5	Hospitalized, not requiring supplemental oxygen - requiring ongoing medical care (COVID-19 related or otherwise)
6	Hospitalized, not requiring supplemental oxygen - no longer requires ongoing medical care
7	Not hospitalized, limitation on activities and/or requiring home oxygen
8	Not hospitalized, no limitations on activities

The lowest value from Day 1 through Day 28 for a patient on the NIAID ordinal scale will be analyzed using the van Elteren test adjusting for the randomization stratification factors. The number need to treat (NNT) to prevent one patient from progressing to level 2 or 1 will be calculated. Mean values will be calculated and differences in treatment effect estimates at Days 7, 14 and 28 will be analyzed. Mean value by treatment group will be plotted over time.

[figure not shown]
Time to the first 2-point improvement on the NIAID scale will be analyzed between treatment groups. The time for subjects who did not achieve 2-point improvement will be censored at day 28 and stratification will be ignored in this analysis. A Kaplan-Meier plot with log-rank test will be used to compare treatment groups.

The stacked bar plot(s) representing the proportion of subjects in each score by treatment arm over time will be generated with stratification ignored. An example of such plot is as follows. The details of the score will be included in the footnote of the plot.

In addition to the stacked bar plot based on the original NIAID scores, another stacked bar plot that lumps NIAID scores into four categories will be generated. The four new categories are:

- a. Death (NIAID score = 1),
- b. IMV/ECMO (NIAID score = 2),
- c. Requiring O₂ or medical care (NIAID scores = 3, 4, 5), and
- d. Not requiring O₂ nor medical care (NIAID scores = 6, 7, 8).

Figure 2.0 Example of a Stacked Bar Plot:

4.12.3.3 28-day Mortality

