4.12.3.4 Length of Hospital Stay

Length of hospital stay will be defined as the number of days hospitalized for at least 1 hour duration.

The length of hospitalization will be analyzed with the Wilcoxon rank-sum test using the van Elteren test adjusting for the randomization stratification factors and will be evaluated through Day 28. The summary will include the median length of hospital stay for the patients who died before Day 28.

Hospital discharge rates at Day 28 will be reported and compared between treatment groups.

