4.14 Subgroup Analyses

The primary end point will be analyzed for the following subgroups:

- Patients who are confirmed SARS-CoV-2 positive and otherwise o age group < 65 and ≥ 65 o sex o BMI < 30 and ≥ 30 o Patients that receive one dose and two doses of study drug o Patients who reach NIAID ordinal scale score = 2 within day 4 and those who do not o Patients with baseline NIAID ordinal scale score of 3, and those with baseline score of 4 or 5
- Patients who received remdesivir and those who do not.

For endpoints which do not consider mortality, subgroup analyses of survivors only may be conducted if appropriate.

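### The log-rank test of time to 2-point NIAID improvement leaves out the baseline NIAID score that defines the event; stratifying by it may recover about 0 to 10 points of power

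*SAP*

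**What the plan says.** SAP 4.12.3.2 adds a time-to-event analysis of the ordinal scale: "Time to the first 2-point improvement on the NIAID scale will be analyzed between treatment groups". On follow-up: "The time for subjects who did not achieve 2-point improvement will be censored at day 28". On the method: "stratification will be ignored in this analysis. A Kaplan-Meier plot with log-rank test will be used to compare treatment groups". No covariate is named, and no hazard ratio is planned. SAP 5.1 lists the result as Table 37 under the secondary objectives.

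Other relevant places:

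- **Randomization.** SAP 3.3: "Patients who meet all criteria for enrollment will be stratified by age group", together with sex and site. The baseline NIAID score is not a factor.
- **Baseline score.** The Schedule of Activities (Protocol section 2) records it at screening. SAP 4.8 only summarizes it. SAP 4.14 uses it to form a subgroup for the primary endpoint: "Patients with baseline NIAID ordinal scale score of 3, and those with baseline score of 4 or 5".
- **Companion analyses.** The lowest NIAID score (same section) and length of stay (SAP 4.12.3.4) are tested with adjustment; for length of stay, "using the van Elteren test adjusting for the randomization stratification factors and will be evaluated through Day 28".
- **Error level.** SAP 4.1: "All tests of treatment effects will be conducted at a 1-sided alpha level of 0.05, unless otherwise stated".

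**The concern.** A two-point gain is a different event for each starting score. A patient at 3 must reach 5, which is still in hospital but off oxygen. A patient at 4 must reach 6. A patient at 5 must reach 7, which means discharge.

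The entry criteria make a mixed baseline likely. Protocol 6.1 accepts either infiltrates on imaging or a room-air saturation of 95% or less, so patients not on oxygen can enter. Protocol 6.2 excludes those needing immediate IMV.

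Two things are at stake. If the starting score predicts how soon the event comes, one pooled risk set compares unlike patients and the log-rank test loses power. And because randomization does not balance the score, a chance imbalance between arms shifts the Kaplan-Meier curves for reasons unrelated to treatment. No other part of the SAP corrects this analysis for baseline.

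**Working it through.** **The plan's own figure.** There is none for this test: no power, event count or hazard ratio is stated. The 81% in SAP 3.2 belongs to the Wilcoxon test of ventilator-free days and is not a benchmark here.

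**Inputs from the documents.** 200 evaluable patients, 1:1 (SAP 3.2: "in order that 200 patients complete the study"); one-sided 0.05; follow-up to Day 28; baseline scores 3, 4 and 5.

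**Inputs assumed.** Rate ratio for improvement 1.45 within strata. Baseline 3/4/5 mix 30/40/30, 25/50/25 or 15/70/15. Age rate ratio 0.65, sex 1.15, site log-SD 0.3. Permuted blocks of 4 within age by sex by site, 8 to 20 sites.

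**Chance imbalance.** If 30% of patients hold a given score (assumed), the between-arm difference in that share has SD √(2 × 0.3 × 0.7 / 100) = 0.065. The 95% range is ±1.96 × 0.065, about ±13 percentage points.

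**Reference power without heterogeneity (Schoenfeld).** Power = Φ(√d × ln(1.45) / 2 − 1.645), where d is the number of events. For d = 138: 11.75 × 0.3716 / 2 − 1.645 = 0.54, giving about 70%. For d = 144: 12 × 0.3716 / 2 − 1.645 = 0.58, giving about 72%.

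**Simulation.** Times are exponential in whole days, with daily rate −ln(1 − p)/28, where p is the assumed placebo probability of improving by Day 28. For starting scores 3/4/5:

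- Strong gradient: p = 40/70/92%, rates 0.018, 0.043, 0.090, about a 5-fold span.
- Moderate gradient: p = 55/70/85%, rates 0.029, 0.043, 0.068, about a 2.4-fold span.
- Flat: p = 70% throughout.

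Power in %, unstratified → stratified. The baseline-only columns used 3,000 trials per setting (Monte Carlo SE about 0.9 points). The last column used 12 sites and 2,000 trials (SE about 1.1).

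| Gradient | Baseline score, 8 sites | Baseline score, 20 sites | Baseline score × age group |
|---|---|---|---|
| Strong | 54.3 → 64.4 | 54.2 → 64.5 | 54.9 → 64.3 |
| Moderate | 64.3 → 66.8 | 63.0 → 65.8 | 63.6 → 67.0 |
| Moderate, 15/70/15 mix | 65.2 → 66.9 | 65.9 → 66.5 | not run |
| Flat | 66.8 → 66.0 | 66.1 → 65.5 | 67.4 → 67.2 |
| Mildly reversed | 67.1 → 66.8 | 66.1 → 65.6 | 65.6 → 65.6 |

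A Cox model with baseline score, age and sex (800 trials, SE about 1.7) agrees in direction: 57 → 68 strong, 62 → 67 moderate, 69 → 71 flat.

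**Type I error.** With no treatment effect the unstratified test rejected in 3.9 to 5.1% of trials, so it is valid or slightly conservative.

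**The randomization strata themselves.** Age by sex alone changed power by 0 to +2 points. Age by sex by site, with the SAP's pooling of small sites, lost 1 to 3 points with 8 sites and about 8 to 10 with 20. The cells explain this: before pooling, 2 × 2 × 8 = 32 cells hold about 6 patients each, and 2 × 2 × 20 = 80 cells hold 2.5. Three baseline levels by two age groups make 6 cells of about 33.

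**The case against.** The strongest reply is that the SAP made a deliberate and sensible choice. SAP 4.1 also ignores stratification for all dichotomous variables, so the simple chi-square and log-rank comparisons are unadjusted while the rank tests and mixed models are adjusted. The adjusted rank tests do not use baseline NIAID either. This stands: the omission is a consistent policy, not an isolated slip.

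A reader might go further and infer that ignoring the randomization strata as such gives power away. The documents and the check do not support that. The strata include site, and stratifying on all of them at this sample size loses power.

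A reader might also infer that the test is biased or that the treatment effect is attenuated. The test holds its level, and no hazard ratio is planned that could be attenuated. In any case, marginal and within-stratum hazard ratios are different quantities.

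Nor is a gain guaranteed. Sicker patients start further back but have the nearer target, still in hospital, while score-5 patients must be discharged. The two could offset each other and leave a flat or mildly reversed gradient, where nothing is gained. Gains as large as 68% to 83% appear only if the rate is assumed to differ 2.5-fold per baseline step (2.5² = 6.25-fold from 3 to 5), with an assumed hazard ratio of 1.5. The documents give no basis for that. Finally, stratifying compares like with like but does not turn three kinds of event into one; that belongs to the endpoint.

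What remains is that a recorded baseline value that defines the event goes unused, and that using it with age group showed no measurable loss in any scenario tried.

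**Conclusion.** The point holds as a minor efficiency and interpretability issue. The log-rank test in SAP 4.12.3.2 is valid, but it leaves out the score that fixes each patient's target state and that randomization does not balance. Stratifying by that score is estimated to gain about 0 to 10 points of power: about 10 with a strong prognostic gradient, about 1 to 3 with a moderate one, none if flat or mildly reversed. The range rests on an assumed rate ratio of 1.45 and on assumed baseline mixes and gradients.

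The consequence is confined to one secondary analysis. The SAP added it: Protocol 10.3.3.2 plans a rank-sum test and categorical changes for this scale. It has no power statement, and SAP 4.6 plans no multiplicity adjustment. The primary test is unaffected.

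**What to change.** Before final unblinding, replace the SAP 4.12.3.2 statement that drops stratification with the following:

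- Primary test for this endpoint: log-rank stratified by baseline NIAID score (3, 4, 5 or higher) and age group (<65, ≥65). Use the same baseline assessment that defines the two-point gain.
- Leave out site and sex, and say why: the cells become sparse. Fix this now rather than after seeing cell counts. In the simulations, adding sex to baseline score and age cost up to about 2 points against the unstratified test when the gradient was flat.
- Report a hazard ratio with 90% CI from a Cox model with the same strata. This supplies the effect estimate that the section lacks, at the confidence level used in SAP 4.1.
- Keep the unstratified log-rank test as a sensitivity analysis and the unstratified Kaplan-Meier plot as the display.

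Because SAP 4.16.1 describes an unblinded interim look, staff who have not seen those results should make the change.

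**Cost.** A short SAP edit and a small programming change, with data already collected. The statistical downside is up to about 1 to 2 points of power if the baseline score turns out not to be prognostic. Since the protocol does not name this analysis, the change does not appear to touch a principal feature that would need a protocol amendment under SAP 4.1.

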4.12.3.4 Length of Hospital Stay

Length of hospital stay will be defined as the number of days hospitalized for at least 1 hour duration.

The length of hospitalization will be analyzed with the Wilcoxon rank-sum test using the van Elteren test adjusting for the randomization stratification factors and will be evaluated through Day 28. The summary will include the median length of hospital stay for the patients who died before Day 28.

Hospital discharge rates at Day 28 will be reported and compared between treatment groups.

4.12.4 Other Efficacy Analyses

Other efficacy endpoints will be described and compared between treatment groups.

4.12.4.1 Pulmonary Function

Pulmonary function will be reported daily as the range of average lowest value for SpO₂ and the highest value of oxygen flow-rate; the FiO₂ will be derived for non-closed systems. The midpoint of the range of average lowest SpO₂ and derived FiO₂ and respiratory rate for each day will be analyzed via MMRM and plotted over time by treatment group. Mean values will be calculated and differences in treatment effect estimates at Days 7, 14 and 28 will be analyzed.

If any subject has multiple FiO₂ records in a day, the maximum of the records of the day will be taken in the analysis; if a subject has multiple respiratory rate records in a day, the mean of the records of the day will be used in the analysis.

However, FiO₂ will only be available for analysis when the patients used the following devices during the study:

- Ventilator (FiO₂ is given directly in the CRF),
- Nasal Cannula (FiO₂ will be calculated using the table listed below),
- Venturi Mask (FiO₂ will be calculated using the table listed below).

FiO₂ (Fraction of Inspired Oxygen) information (from louisville.edu, for reference only):

For all supplemental oxygen delivery devices, the patient is not just breathing the direct oxygen, but rather is breathing a combination of room air plus the oxygen from the supplemental device. Different devices deliver to the patient more or less of a % of what is coming in from the tank.

Fraction of Inspired Oxygen (FiO₂) for a nasal cannula and a Venturi mask are given in the tables below. For other oxygen delivery systems, such as masks, tents, there is more oxygen that "blows by" or is lost, therefore higher flow rate setting on the oxygen tank are needed to achieve the same FiO₂. A tracheostomy would require different calculations as well.

Example: with a nasal cannula, we assume that the fraction of oxygen that is inspired (above the normal atmospheric level or 20%) increases by 4% for every additional liter of oxygen flow administered.

For a Nasal Cannula:

Oxygen tank FLOW RATE in liters / min	FiO₂ -- Fraction of Inspired Oxygen value
0 (no oxygen, just room air)	.20
1 L / min	.24
2 L / min	.28
3 L / min	.32
4 L / min	.36
5 L / min	.40
6 L / min	.44

For a Venturi Mask:

Oxygen tank FLOW RATE in liters / min	FiO₂ – Fraction of Inspired Oxygen Value
0 (no oxygen, just room air)	.20
4 L / min	.26
6 L / min	.31
8 L / min	.375
12 L / min	.447

4.12.4.2 Supportive Care

The following types of supportive care will be analyzed: ECMO, IMV, ECMO or IMV, noninvasive ventilation; and/or high-flow oxygen, any of the previous 4 types of care, proning, tracheostomy, COVID-19 convalescent plasma, and remdesivir use. The percent of patients who ever receive each of these and the number of days each of these is given, during Days 1-28, will be analyzed between treatment groups.

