6.1. Inclusion Criteria

Patients are eligible to be included in the study only if they meet all of the following criteria at screening, unless specified otherwise:

1. Must be admitted to the hospital
2. Confirmed pneumonia with:
 - a. Presence of signs and symptoms of respiratory disease (ie, cough, tachypnea, and/or shortness of breath)
and at least one of the following
 - b. Infiltrates on chest imaging
 - c. oxygen saturation (SpO₂) of $\leq 95\%$ on room air
3. With presumed or confirmed COVID-19
4. Are at least 18 years of age at the time of randomization.
5. Are able and willing to give signed informed consent (legally authorized representative can provide informed consent if needed).

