6.2. Exclusion Criteria

Patients will be excluded from study enrollment if they meet any of the following criteria at screening, until specified otherwise:

1. Have ARDS and/or require immediate intermittent mandatory ventilation (IMV).
2. In the opinion of the investigator, is moribund irrespective of the provision of treatments.
3. Any concurrent serious medical condition (e.g. patients with estimated glomerular filtration rate [eGFR] < 15 mL/min/1.73m² or on dialysis, preexisting lung disease requiring O₂ at rest, a body mass index [BMI] that precludes techniques such as proning) or concomitant medication that in the opinion of the investigator that would preclude participation in the study.
4. Have received treatment with a drug predominantly targeting Ang2 activity (e.g., tyrosine kinase inhibitors and/or antibody treatment) within the past month or 5 half-lives, whichever is longer.
5. Have a known sensitivity to mAbs or other therapeutic proteins, to agents of similar biologic composition as LY3127804, or to any products used in the formulation of LY3127804 (refer to the IB for LY3127804 for details) or are incompatible with the treatment of LY3127804.

6. Have a known history or show evidence of human immunodeficiency virus (HIV) and/or hepatitis A, B or C
7. Exclusion Criterion [7] has been deleted.
8. Have a significant bleeding disorder or active vasculitis or had a Grade ≥ 3 bleeding episode within 12 weeks prior to receiving treatment
9. Have experienced any arterial thromboembolic event, including myocardial infarction, unstable angina, cerebrovascular accident, or transient ischemic attack, within 6 months prior to receiving treatment
10. Have experienced any Grade 3 or 4 venous thromboembolic event that is considered by the investigator to be life-threatening or that is symptomatic and not adequately treated by anticoagulation therapy within 6 months prior to receiving treatment. Patients with chronic portal vein thrombosis who are asymptomatic and not considered to need anticoagulation therapy are eligible.
11. Have chronic congestive heart failure (New York Heart Association class ≥ 3) or uncontrolled cardiac dysrhythmia
12. Have a serious nonhealing: (a) wound, (b) peptic ulcer, or (c) bone fracture, within 28 days prior to receiving first dose of study drug

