4.11 Concomitant Therapy

Concomitant medications will be defined as medications taken on or after the date of the first dose of study treatment. This includes all medications initially taken prior to the date of first dose of study treatment but with a stop date that is either missing or after the date of first dose of study treatment. Those medications where the stop date is documented as prior to the date of first dose of study treatment will be classified as prior medications. The prior medications will not be included in any summary reports.

Concomitant medications will be summarized and will be presented by anatomical therapeutic chemical drug classes (ATC level 4) using the latest version of the WHO drug dictionary.

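### Non-invasive ventilation or high-flow oxygen already running at first dose counts as a Day 1–28 outcome, and COVID-19 drugs completed before first dose appear in no summary by arm

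*SAP*

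**What the plan says.** **Supportive care.** SAP 4.12.4.2 lists ECMO, IMV, either of these, non-invasive ventilation and/or high-flow oxygen, a composite of those four, and then "proning, tracheostomy, COVID-19 convalescent plasma, and remdesivir use". For each it analyses "The percent of patients who ever receive each of these and the number of days each of these is given, during Days 1-28". It has no rule for support already in place at first dose. SAP 4.1 tests dichotomous variables with a chi-square test that ignores stratification. SAP 4.4 gives patients who die the worst outcome in these analyses.

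**Who may enter.** SAP 4.14 plans a primary-endpoint subgroup analysis of "Patients with baseline NIAID ordinal scale score of 3, and those with baseline score of 4 or 5". On the scale in SAP 4.12.3.2, score 3 means non-invasive ventilation or high-flow oxygen. Protocol 6.2 excludes patients who have ARDS or need IMV immediately. The first inclusion criterion in Protocol 6.1 is "Must be admitted to the hospital", with no limit on time in hospital before enrolment.

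**Medications.** Under SAP 4.11 a drug whose "stop date is documented as prior to the date of first dose of study treatment will be classified as prior medications", and "The prior medications will not be included in any summary reports". A drug begun earlier but "with a stop date that is either missing or after the date of first dose of study treatment" is concomitant and is summarised. Neither the baseline characteristics in SAP 4.8 nor the tables in SAP 5.1 include COVID-19 therapy received before first dose.

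**The concern.** The ever-received percentage is compared between arms as an efficacy outcome (SAP 4.12.4, Table 43). For non-invasive ventilation or high-flow oxygen it mixes support that the study drug could have prevented with support that was already running. The composite inherits the problem: a patient who enters on high-flow oxygen is already an event, so later escalation to IMV adds nothing to that row. Proning may be affected too, though the documents do not say whether any patient enters proned.

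The medication rule causes a different loss. A COVID-19 treatment completed the day before first dose appears in neither a baseline nor a concomitant-medication summary. If it was convalescent plasma or remdesivir, the patient also counts as a non-recipient in SAP 4.12.4.2. A chance imbalance between arms in such treatment could not be seen in those summaries when the results are read.

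**Working it through.** **Plan's own figure.** The plan states no rate or power for the supportive-care analyses. Its only power figure is 81% for the primary Wilcoxon test (SAP 3.2), and nothing here depends on it. A tie-corrected recalculation on three outcome values (−1, one intermediate value chosen to give a mean difference of 3.0 days, and 28) gives 73% if all deaths occur in ventilated patients, 90% if none do, and 81.3% if about 60% do. The figure is attainable, but it cannot be confirmed because the overlap is not stated.

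**Inputs for the dilution check.**
- From the documents: 100 per arm (SAP 3.2) and one-sided alpha 0.05 (SAP 4.1).
- Borrowed as an illustration: new-onset rates p0 = 25% on placebo and p1 = 12.5% on drug. These are the IMV assumptions in SAP 3.2; the documents give no rate for non-invasive ventilation or high-flow oxygen.
- Assumed: b, the share already on the support at first dose, equal in both arms as randomisation gives in expectation. Range 0 to 50%.

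**Formulas.** Everyone on the support at baseline is an event, so the ever-received rate is b + (1 − b)p. The difference is (1 − b)(p0 − p1), and the ratio is [b + (1 − b)p1] / [b + (1 − b)p0]. Power for two proportions, pooled variance under the null and unpooled under the alternative:

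Φ{ [√n(P0 − P1) − 1.645√(2P̄(1 − P̄))] / √(P0(1 − P0) + P1(1 − P1)) }

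The planned analysis uses all n = 100 per arm. The alternative uses the 100(1 − b) per arm not on that support at baseline.

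**Worked case, b = 20%.** P0 = 0.20 + 0.80 × 0.25 = 0.40 and P1 = 0.20 + 0.80 × 0.125 = 0.30. The difference is 10 points, the ratio 0.75 and the power 43.5%. New initiation only, 80 per arm: difference 12.5 points, ratio 0.50, power 65.0%.

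| b | Planned: rates | Difference (points) | Ratio | Power | New initiation only (12.5 points, ratio 0.50): power |
|---|---|---|---|---|---|
| 0 | 25.0% vs 12.5% | 12.5 | 0.50 | 73.5% | 73.5% |
| 10% | 32.5% vs 21.25% | 11.25 | 0.65 | 56.0% | 69.5% |
| 20% | 40.0% vs 30.0% | 10.0 | 0.75 | 43.5% | 65.0% |
| 30% | 47.5% vs 38.75% | 8.75 | 0.82 | 34.6% | 60.0% |
| 40% | 55.0% vs 47.5% | 7.5 | 0.86 | 27.9% | 54.4% |
| 50% | 62.5% vs 56.25% | 6.25 | 0.90 | 22.8% | 48.2% |

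**Other assumed rates.** At 40% vs 20% and b = 20%, the difference is 16 rather than 20 points and power is 74.0% rather than 87.3%. At 30% vs 20%, b = 10, 20, 30 and 40% gives differences of 9, 8, 7 and 6 points and ratios of 0.76, 0.82, 0.86 and 0.90.

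**Limit of the arithmetic.** All of this is before the SAP 4.4 death rule. Counting deaths as events changes the rates. For example, 20% use among survivors in both arms with the planned mortality gives 0.125 + 0.875 × 0.20 = 30% on placebo and 0.0625 + 0.9375 × 0.20 = 25% on drug. The percentages above are therefore not what Table 43 would print.

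**Medications.** No arithmetic applies. A plasma infusion given and completed the day before first dose has a documented stop date before first dose. SAP 4.11 makes it prior and bars it from summaries. It lies outside Days 1–28, so SAP 4.12.4.2 counts non-receipt. SAP 4.8 has no item that would show it.

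**The case against.** Much of the case on the other side stands, and it limits the point.

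- **Not every row is diluted.** A reader might infer that all supportive-care comparisons are affected. The screening exclusion puts IMV, ECMO and, in practice, tracheostomy close to b = 0, where the two analyses coincide. Only patients who worsen between screening and dosing would differ.
- **Days of support remain valid.** For a patient who enters on high-flow oxygen, days of support after first dose are something treatment can shorten. The dilution concerns the ever-received percentage.
- **Remdesivir and plasma are co-interventions.** Their use during Days 1–28 describes background care; it is not an escalation outcome that the study drug should prevent.
- **Prior therapy is not wholly invisible.** Only courses with a documented earlier stop date are barred. Ongoing courses and missing stop dates count as concomitant, SAP 4.3.3 resolves doubtful dates the same way, and listings are not barred. The remdesivir subgroup has no time window, so earlier completed use is undefined there rather than dropped.
- **IL-6 antagonists are not in the SAP 4.12.4.2 list.** A reader might infer that prior use counts as non-receipt there. It does not; for these drugs the only loss is omission from summaries.
- **Escalation is examined elsewhere.** Complete response (SAP 4.12.3.1) and the worst NIAID score (SAP 4.12.3.2) cover it, and SAP 4.8 summarises baseline NIAID score and FiO₂ by arm, so baseline non-invasive ventilation or high-flow oxygen can be seen.

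These points leave two things unanswered: the ever-received comparison still mixes baseline and new support in the rows where b is not zero, and completed pre-dose COVID-19 drugs still appear in no baseline or concomitant-medication summary by arm.

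**Conclusion.** The point holds in two parts.

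First, the ever-received comparison for non-invasive ventilation or high-flow oxygen, its composite and possibly proning is attenuated by the factor (1 − b) before the death rule. In the main illustration the planned analysis has 13.5 to 26.5 points less power than a new-initiation analysis for b between 10% and 50%. The factor follows exactly from the definition; b and the new-onset rates are assumptions.

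Second, COVID-19 drugs with a documented stop before first dose are kept out of all summaries by explicit text, and completed plasma or remdesivir also counts as non-receipt during Days 1–28.

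A reader might infer bias, an inflated type I error or damage to the primary result. The documents do not support that. Randomisation balances baseline support in expectation, so the consequence is lost power, and the affected rows are other-efficacy analyses. The change is worth making because it is cheap and the rules as written give a less informative answer.

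**What to change.** 1. **SAP 4.12.4.2 and Table 43.** For non-invasive ventilation or high-flow oxygen, the composite and proning, show support present at first dose as a baseline row. Compare new initiation after first dose among patients not on that support at baseline. Because baseline status defines this group, the randomised comparison is kept. Retain the number-of-days analysis.
2. **Remdesivir and convalescent plasma.** Keep Days 1–28 use as a description of co-intervention, split into started before and started after first dose.
3. **SAP 4.11 and 4.8.** Lift the bar for COVID-19-directed drugs and tabulate those received before first dose by arm with the baseline characteristics.
4. **SAP 4.14.** State the time window that defines receipt in the remdesivir subgroup (Table 34).

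**Cost.** SAP wording, one extra table and a smaller denominator in the new-initiation rows. Start and stop dates are needed for COVID-19 drugs completed before first dose. The Protocol's Schedule of Activities collects concomitant medications from Day 1, and SAP 4.16.1 describes the interim analysis as already done, so some of these dates may have to be collected retrospectively.
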